### **9.3. Vital Sign Measurements**

Vital signs include body temperature (aural), blood pressure (after 5 minutes resting), respiration rate, and pulse rate (after 5 minutes resting).

Descriptive statistics will be applied to summarize observed values, change from baseline values.

By-subject listing will be produced for vital signs.

### **9.4. Electrocardiograms**

Electrocardiogram (ECG) parameters to be recorded are: heart rate, QT interval, PR interval, QRS interval, RR interval, and QTc (corrected) using the Fridericia correction.

The ECG will be summarized in descriptive manner including the changes from baseline by visit.

The overall ECG interpretation by investigator (or designee) in categories of ‘within normal limits’, ‘abnormal but not clinically significant’, and ‘abnormal with clinically significance’ will be summarized by visit, the shift from baseline to worst status during the treatment in the overall ECG interpretation will be displayed in cross-tabulations by visit.

The source values of the ECG parameter will be listed by subject, and visit.

### **9.5. Events Related to the COVID-19 Public Health Emergency**

Missed or altered visits due to the COVID-19 public health emergency will be recorded in specific eCRF, diagnosed COVID-19 cases will be recorded as AE or SAE, and these data will be presented in listings.

## 10. PHARMACOKINETICS AND PHARMACODYNAMICS

### 10.1. Pharmacokinetic Analysis

#### 10.1.1. Pharmacokinetic Sample Concentrations

Blood samples from sparse and dense sampling schedules will be collected and analyzed for investigational products (LC350189) in plasma as outlined in Section 14.2.

Individual plasma concentrations and time deviation data for investigational products (LC350189) will be listed by treatment using the safety set. Individual plasma concentration versus actual time profiles will be plotted on both linear and semi logarithmic scales for each subject using the safety set.

Plasma concentration data will be summarized by time point for each treatment using the following descriptive statistics for the PK analysis set: number of subjects in a given treatment group (N), number of non-missing observations (n), arithmetic mean, arithmetic standard deviation (SD), arithmetic coefficient of variation (CV%), geometric mean, geometric CV%, median, minimum, and maximum values. Plasma concentrations will be reported to 3 significant figures in summary statistics except for CV% which will be reported to 1 decimal place.

Plasma LC350189 concentrations that are below the limit of quantification (BLQ) will be set to zero for calculation of summary statistics for concentration data at each timepoint.

Geometric mean and geometric CV% will be set to missing if minimum is zero. Mean plasma concentration versus nominal time profiles will be plotted using the PK analysis set on both linear and semi-logarithmic scales.

In addition, individual trough levels of investigational products (LC350189) collected before dosing on Days 1, 14, 28, 56 and 84 will be plotted for each treatment on both linear and semi-logarithmic scales for each subject using the PK analysis set and mean trough concentration versus nominal time profiles will be plotted for each treatment using the PK analysis set on both linear and semi-logarithmic scales.

For subjects randomized into the active control group (febuxostat) before the implementation of the Protocol version 5.0, febuxostat concentration data will be listed.

#### 10.1.2. Pharmacokinetic Parameters

The individual plasma concentration versus actual time data for LC350189 and febuxostat will

| PK Parameter                     | Definition  |
|----------------------------------|---|
| Sparse and Dense Sampling |   |
| C trough,ss           | Plasma concentration observed at the end of a dosing interval [collected before the next administration].   |
| Dense Sampling            |   |
| C max                 | Maximum observed concentration in plasma  |
| T max                 | Time to maximum concentration in plasma   |
| t 1/2                 | Apparent terminal elimination half-life, calculated as $[\ln(2) / \lambda_z]$ ; if data permits   |
| AUC 0-t               | Area under the concentration versus time curve (AUC) from time 0 to the last quantifiable concentration, calculated using the linear-up/log-down trapezoidal rule |
| AUC 0-8h              | AUC from time 0 to 8 hours post dose, calculated by the linear-up/log-down trapezoidal rule   |
| AUC 0-12h             | AUC from time 0 to 12 hours post dose, calculated by the linear-up/log-down trapezoidal rule  |

For the calculation of PK parameters, all plasma concentrations that are BLQ prior to the first measurable concentration will be set to zero. The BLQ values that are between measurable concentrations will be set to missing. If two or more consecutive BLQ concentrations are followed by quantifiable concentrations, these quantified values will be set to missing. The BLQ values following the last quantifiable time-points will be set to missing except the first BLQ can be set to 1/2 the lower limit of quantification if needed to facilitate the terminal phase slope estimation. No concentration estimates will be imputed for missing sample values. Any sample

with a missing value will be treated as if the sample had not been scheduled for collection and will be ignored when calculating mean concentrations or PK parameters.

AUC values will be calculated by numeric integration using linear trapezoidal linear interpolation rule.

The individual PK parameters of investigational products (LC350189 and febuxostat) will be presented in a data listing. The PK parameters of LC350189 will be summarized using the following descriptive statistics: N, n, arithmetic mean, SD, median, CV%, minimum, and maximum. Note that mean, SD and CV% will not be presented for Tmax. Geometric means and geometric CV% will also be included for AUC and Cmax values.

Plasma PK parameters will be displayed to 3 significant figures in all data listings and summary tables.

## 10.2. Pharmacodynamic Analysis

### 10.2.1. Serum Uric Acid Concentrations

Blood samples will be collected and analyzed for sUA as outlined in Section 14.2.

Serum uric acid concentrations that are below the limit of quantification (BLQ) will be set to zero for calculation of summary statistics for sUA concentration data at each timepoint.

Individual serum concentrations for sUA will be listed by treatment using the FAS and PPS for original, change from baseline, and percent change from baseline. Individual serum sUA concentration versus actual time profiles will be plotted on both linear and semi logarithmic scales for each subject using the FAS and PPS (original, change from baseline, and percent change from baseline).

Serum concentration data for sUA will be summarized by time point for each treatment using the following descriptive statistics for FAS and PPS: N, n, arithmetic mean, arithmetic SD, arithmetic CV%, geometric mean, geometric CV%, median, minimum, and maximum values for original scale, change from baseline, and percent change from baseline. Baseline will be pre-dose concentration for Visit 4 (Day 1). Mean serum uric acid concentration versus nominal time profiles will be plotted using the FAS and PPS on both linear and semi-logarithmic scales (original, change from baseline, and percent change from baseline).

In addition, individual trough levels of sUA collected before dosing on Days 1, 14, 28, 56 and 84 will be plotted for each treatment on both linear and semi-logarithmic scales for each subject and mean trough concentration versus nominal time profiles will be plotted for each treatment using the FAS and PPS on both linear and semi-logarithmic scales.

### 10.2.2. Pharmacodynamic Parameters

The individual serum concentration versus actual time data for sUA and change from baseline sUA will be used to derive the following PD parameters using non-compartmental analysis, using Phoenix® WinNonlin® (Certara USA, Inc., Princeton, NJ, 8.0 or higher) or SAS® software (SAS Institute, Inc., Cary, NC, Version 9.4 or higher).

| PD Parameter                     | Definition  |
|----------------------------------|---|
| Sparse and Dense Sampling |   |
| $C_{trough,ss}$                  | Serum concentration observed at the end of a dosing interval (collected before the next administration).                                    |
| PD Parameter              |   |
| Dense Sampling            |   |
| $E_{max}$                        | Maximum observed effect   |
| $TE_{max}$                       | Time to maximum observed effect   |
| $AUEC_{0-t}$                     | Area under effect curve (AUEC) from time 0 to the last quantifiable concentration, calculated using the linear-up/log-down trapezoidal rule |
| $AUEC_{0-8h}$                    | AUEC from 0 to 8 hours post-dose calculated using the linear-up/log-down trapezoidal rule   |
| $AUEC_{0-12h}$                   | AUEC from 0 to 12 hours post-dose calculated using the linear-up/log-down trapezoidal rule  |

For the calculation of PD parameters, all sUA concentrations that are BLQ prior to the first measurable concentration will be set to zero. The BLQ values that are between measurable concentrations will be set to missing. If two or more consecutive BLQ concentrations are followed by quantifiable concentrations, these quantified values will be set to missing. The BLQ values following the last quantifiable time-points will be set to missing except the first BLQ can be set to 1/2 the lower limit of quantification if needed to facilitate the parameter estimation.

AUEC values will be calculated by numeric integration using linear trapezoidal linear interpolation rule.

Serum PD parameters will be presented in data listings and summarized using descriptive statistics (n, arithmetic mean, SD, CV%, median, minimum, and maximum) by treatment on the original scale and change from baseline/percent change from baseline scale. Note that mean, SD and CV% will not be presented for  $TE_{max}$ . Geometric means and geometric CV% will also be included for AUEC and  $C_{max}$  values.

Serum PD parameters will be displayed to 3 significant figures in all data listings and summary tables.

### **10.3. Exploratory Pharmacodynamic Analysis**

#### **10.3.1. Serum Hypoxanthine and Xanthine Concentrations**

Blood samples will be collected and analyzed for hypoxanthine and xanthine at baseline (Visit 4) and Day 84 (Visit 8).

Serum concentration data for hypoxanthine and xanthine will be summarized by change from baseline for each treatment using the following descriptive statistics for PPS: N, n, arithmetic mean, arithmetic SD, arithmetic CV%, geometric mean, geometric CV%, median, minimum, and maximum values. Serum hypoxanthine and xanthine concentrations that are BLQ will be set to zero for calculation of summary statistics for concentration data at each timepoint.

## **11. INTERIM ANALYSIS**

No formal interim analysis is planned.

## **12. CHANGES TO THE PLANNED ANALYSIS**

No changes to the statistical analyses section of the protocol are made in this SAP.

## 14. APPENDICES

### 14.1. Schedule of Assessments

| Study Period                           | SCREENING & WASH-OUT/PROPHYLAXIS  |                       |                | TREATMENT PERIOD  |             |             |             | FOLLOW-UP    |              |
|--|---|-----------------------|----------------|-------------------------------|-------------|-------------|-------------|--------------|--------------|
|  |   |                       |                | -                             |             |             |             |              |              |
| Visit number                                       | 1   | 2                     | 3              | 4                             | 5           | 6           | 7           | 8            | 9            |
| Time point (Weeks)                                 | -5 to -3                          | -5 to -3  | -2 to -1       | 1                             | 2           | 4           | 8           | 12           | 14           |
| Time point (Days)                                  | -33 to -26                                    | -30 to -23            | -9 to -4       | 1                             | 14
(±2D) | 28
(±2D) | 56
(±2D) | 84
(±2 D) | 98
(±2 D) |
| Informed consent                                   | X   |                       |                |                               |             |             |             |              |              |
| Assess eligibility criteria                        | X                                 | X                     |                | X                 |             |             |             |              |              |
| Demographics                                       | X   |                       |                |                               |             |             |             |              |              |
| Medical history                                    | X   |                       |                |                               |             |             |             |              |              |
| Physical examination                               | X   |                       |                |                               |             |             |             |              |              |
| Height   | X   |                       |                |                               |             |             |             |              |              |
| Weight, BMI  | X   |                       |                | X                             | X           | X           | X           | X            | X            |
| Tophi assessment                                   | X   |                       |                |                               |             |             |             | X            |              |
| Pregnancy test                         | X                                 |                       |                | X                             | X           | X           | X           | X            |              |
| Hep B, Hep C, HIV test                             | X   |                       |                |                               |             |             |             |              |              |
| Record prior  /concomitant medications | X   |                       | X              | X                             | X           | X           | X           | X            | X            |
| 12-lead ECG  | X   |                       |                | X                             |             |             |             | X            |              |
| Vital signs  | X                                |                       | X              | X                | X           | X           | X           | X            | X            |
| Blood sampling for endpoints and laboratory tests  | X                                 |                       | X  | X                | X           | X           | X           | X            |              |
| Blood sampling for PK/PD              |   |                       |                | X                             | X           | X           | X           | X            |              |
| Urine sampling - urinalysis                        | X   |                       | X              | X                             | X           | X           | X           | X            |              |
| sUA blood sampling for randomization               |   |                       | X  |                               |             |             |             |              |              |
| Randomization                                      |   |                       |                | X             |             |             |             |              |              |
| Dispense prophylaxis                  |   | X                     |                | X                             |             | X           | X           |              |              |
| Dispense study drug                                |   |                       |                | X                             |             | X           | X           |              |              |
| Collect unused prophylaxis                         |   |                       |                | X                             |             | X           | X           | X            |              |
| Collect unused study drug                          |   |                       |                |                               | X           | X           | X           | X            |              |
| Drug accountability/compliance                     |   |                       |                | X                |             | X           | X           | X            |              |
| Assess and record adverse events                   | X   | X                     | X              | X                             | X           | X           | X           | X            | X            |
| Gout Flare eDiary                     |   | X        | X              | X                             | X           | X           | X           | X            |              |
| eDiary device return                               |   |                       |                |                               |             |             |             | X            |              |

. Subjects should attend all Visits following a fast for at least 8 hours except visit at Day 98 (Visit 9).

. All efforts should be made to maintain protocol-defined visit windows, but if an extenuating circumstance arises preventing this, the Sponsor and/or designee should be consulted. If the Sponsor and/or designee determine that the scientific integrity of data and subject safety would not be compromised, an out of window visit may be permitted.

. Subjects will be instructed to withhold the investigational products on Visit days.

. Screening Visit will be between Day -33 to -26; prophylaxis will start between Day -30 to -23, once a subject is confirmed eligible. Subjects will be instructed to discontinue their current ULT the same day they begin prophylaxis if they are on ULT at screening.

. Single retest is permitted during the screening period if the investigator believes there is an appropriate rationale to perform a retest, which is believed to be due to an intercurrent condition and does not present a safety issue for the subject to participate in the study, and all efforts should be made to maintain protocol-defined visit windows.

. Gout per ACR criteria will be confirmed.

. Female with childbearing potential only, urine pregnancy test except Screening Visit (Visit 1).

. Serum pregnancy test.

. Any medications that are started before the first randomized study dose date will be prior medications.

. A single repeat measurement is permitted at screening for eligibility determination.

. On Day 1, vital signs will be taken pre-dose and at 4 hours post-dose.

. Pre-dose sUA (Day 1; Visit 4) will be used as baseline throughout the study.

. Refer to Table 14.2 for PK/PD sampling schedule time points.

. sUA inclusion criterion of  $\geq 8.0\text{mg/dL}$  to  $\leq 12.0\text{mg/dL}$  must be met from the blood sample taken at Day -9 to -4 (Visit 3).

. Subjects who have gout flare during the screening and wash-out/prophylaxis period will not be randomized; the subjects can be rescreened once 3 weeks after resolution of gout flare.

. Prophylaxis with colchicine (0.6 mg QD) will be started at Day -30 to -23, once a subject is confirmed eligible, and will continue through the end of the treatment period.

. Accountability for Colchicine only.

. A gout flare will be defined as an episode of patient-reported acute articular or bursal pain that occurs at rest and is typical of past gout attacks. In addition, both of the following criteria must be met: the intensity of pain at rest must be  $\geq 4$  on an 11-point

numerical rating scale, and the pain must be determined by the patient and/or the Investigator to require anti-inflammatory/analgesic treatment. Finally, at least 2 of 3 possible joint symptoms (swelling, warmth, or tenderness) must be present, and at least 1 of the following must be present: rapid onset of pain, decreased range of joint motion, or joint redness. These parameters will be captured and evaluated by the electronic patient diary (eDiary).

 Device distribution and training on eDiary record will be provided to the subjects.

## 14.2. PK/PD Sampling Schedule

| PK/PD data  | Subjects  | Time point   |
|-------------|---|--|
| Sparse data | All subjects  | 
 
Pre-dose, 4 hours post-dose at Day 1 (Visit 4)
 
Pre-dose at Day 14 (Visit 5)
 
Pre-dose at Day 28 (Visit 6)
 
Pre-dose and 4 hours post-dose at Day 56 (Visit 7)
 
Pre-dose at Day 84 (Visit 8)
 
                 |
| Dense data  | Subjects who sign written informed consent for dense PK/PD sampling | 
 
Pre-dose, 2, 4, 8 and 12 hours post-dose at Day 1 (Visit 4)
 
Pre-dose at Day 14 (Visit 5)
 
Pre-dose at Day 28 (Visit 6)
 
Pre-dose and 4, 8 hours post-dose at Day 56 (Visit 7)
 
Pre-dose at Day 84 (Visit 8)
 
 |

## 14.3. Handling of Dates

Dates will be stored as numeric variables in the SAS analysis files and reported in DDMMYY format (i.e., the Date9. datetime format in SAS).

No imputation will be applied to incomplete or partial date.

### 14.3.1. Calculation Using Dates

Calculations using dates (e.g., subject's age or relative day after the first dose of study drug) will adhere to the following conventions:

Study days after the start day of study drug will be calculated as the difference between the date of interest and the first date of dosing of study treatment plus 1 day. The generalized calculation algorithm for relative day is the following:

- If Target Date  $\geq$  Start Date, then Study Day = (Target Date - Start Date) + 1;
- Else Study Day = (Target Date - Start Date);

Note that Study Day 1 is the first day of treatment of study drug. Negative study days are reflective of observations obtained during the baseline/screening period.

- Intervals that are presented in weeks will be transformed from days to weeks by using (without truncation) the following conversion formula of Weeks = Days /7
- Intervals that are presented in months will be transformed from days to months by using (without truncation) the following conversion formula of Months = Days /30.4167

### 14.3.2. Handling of Incomplete Dates

When date of an event is incomplete (missing Year, Month, or Day), following rules will be applied in comparison:

- If the event start date is clearly on or after the Study Day 1 (i.e. Month of event  $\geq$  Month of Study Day 1 or Year or event  $\geq$  Year of Study Day 1), the medication is categorized as concomitant;
- If the event end date is clearly before the Study Day 1, (i.e. Month of event  $<$  Month of Study Day 1 or Year or event  $<$  Year of Study Day 1), the medication is categorized as prior;
- Otherwise, the medication is categorized as prior/concomitant;
- In case of start date is after end date, a query will be raised.

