#### 7.1.2. Concomitant Medications

Concomitant medication is any medication given in addition to the investigational product(s), including over-the-counter medications, herbal medications, and vitamin supplements, that administered between screening and follow-up, as Medication End Date is on or after Study Day 1. In case of incomplete date, refer the methods specified in Section 14.3.2.

A medication will be categorized as “Prior/Concomitant” if it started before Study Day 1 and ended after Study Day 1. If a medication is taken on the Study Day 1, it will be counted as a concomitant medication.

Prior/Concomitant medications will be included in both summary for prior medications and summary for concomitant medications.

A summary showing the number and percentage of subjects who took concomitant medications will be presented by ATC level 2/level 4 and standardized medication name, using WHODD, for the Safety Set.

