**Determination of prior or concomitant medications:**

|              |               | Start Date   |             |               |               |               |          |               |             |
|--------------|---------------|--------------|-------------|---------------|---------------|---------------|----------|---------------|-------------|
| End Date     |               | Year Missing | Year < YEAR | Year =YEAR    |               |               |          |               | Year > YEAR |
|              |               |              |             | Month Missing | Month < MONTH | Month = MONTH | Day =DAY | Month > MONTH |             |
| Year Missing | Prior/Con     | Prior/Con    | Prior/Con   | Prior/Con     | Prior/Con     | Prior/Con     | Con      | Con           | Con         |
| Year < YEAR  | Prior         | Prior        | N/A         | N/A           | N/A           | N/A           | N/A      | N/A           | N/A         |
| Year =YEAR   | Month Missing | Prior/Con    | Prior/Con   | Prior/Con     | Prior/Con     | Prior/Con     | Con      | Con           | N/A         |
|              | Month < MONTH | Prior        | Prior       | Prior         | Prior         | N/A           | N/A      | N/A           | N/A         |
|              | Month = MONTH | Prior/Con    | Prior/Con   | Prior/Con     | Prior/Con     | Prior/Con     | Con      | N/A           | N/A         |
|              | Day =DAY      | Prior/Con    | Prior/Con   | Prior/Con     | Prior/Con     | Prior/Con     | Con      | N/A           | N/A         |
|              | Month > MONTH | Prior/Con    | Prior/Con   | Prior/Con     | Prior/Con     | Prior/Con     | Con      | Con           | N/A         |
| Year > YEAR  | Prior/Con     | Prior/Con    | Prior/Con   | Prior/Con     | Prior/Con     | Prior/Con     | Con      | Con           | Con         |

- Year/Month/Day: Year, Month, and Day of the event date;
- YEAR/MONTH/DAY: Year, Month, and Day of the Study Day 1;
- Except the scenario of Day=DAY, day of event date are missing;

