**Determination of TEAEs:**

- Year of AE start date is missing, set it as TEAE unless AE end date is clearly earlier than Study Day 1;
- Year of AE start date < Year of Study Day 1, set it as non TEAE;
- Year of AE start date = Year of Study Day 1:
  - If Month of AE start date < Month of Study Day 1, set it as non TEAE;
  - If Month of AE start date = Month of Study Day 1, set it as TEAE unless AE end date is clearly earlier than Study Day 1;
  - If Month of AE start date > Month of Study Day 1, set it as TEAE;
- Year of AE start date > Year of Study Day 1, set it as TEAE;

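### In SAP 14.3.2 the bracketed rules for incomplete medication dates compare month or year without taking the year first, and contradict the table beneath them

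*SAP*

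**What the plan says.** SAP 7.1.1 calls a medication prior if it started before the first dose. SAP 7.1.2 calls it concomitant according to its end date ("as Medication End Date is on or after Study Day 1"). A medication that qualifies as both is counted in both summaries. Both sections send incomplete dates to SAP 14.3.2, and SAP 14.3 rules out imputing them.

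SAP 14.3.2 then gives two instructions.

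- **Three bullets.** The first ("If the event start date is clearly on or after the Study Day 1 (i.e. Month of event" …) labels a record concomitant if the start month is at or after the Day 1 month, or the start year is at or after the Day 1 year. The second ("If the event end date is clearly before the Study Day 1, (i.e. Month of event" …) labels it prior if the end month is before the Day 1 month, or the end year is before the Day 1 year. In both, the month and year tests are joined in the same way: "Month of Study Day 1 or Year or event". The third is the default: "Otherwise, the medication is categorized as prior/concomitant".
- **A table**, headed "Determination of prior or concomitant medications". It crosses end-date categories with start-date categories and looks at the month only when the year equals the Day 1 year. Its footnote sets its scope: "Except the scenario of Day=DAY, day of event date are missing".

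Nothing says whether the bullets or the table govern, or which bullet wins if both apply.

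**The concern.** A month test detached from the year can give the wrong answer: January 2021 has a smaller month number than November 2020 but comes after it. An equal year or month is also not clearly on or after Day 1, because the date may fall earlier in that year or month. If the brackets are programmed literally, a medicine taken on treatment can be filed as prior only, and a medicine stopped before Day 1 as concomitant. At stake is the accuracy of two descriptive tables, and whether two programmers working from the same section would produce the same ones.

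**Working it through.** **Inputs.** The two bracketed conditions, the default bullet and the table, all from SAP 14.3.2, and the counting rule in SAP 7.1.2. The plan states no figure to reproduce.

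**Layout of the table.** It has eight start-date columns and eight end-date rows: year missing; year earlier; same year with month missing, month earlier, month equal, day equal or month later; and year later. As extracted, three rows carry one extra cell, read here as a merged-header artefact. The cells that are not N/A, row by row, are 8 + 2 + 7 + 4 + 6 + 6 + 7 + 8 = 48.

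**Literal reading, bullets in printed order.** Cells where the bullets can give a label different from the table:

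| Start date | Conflicting cells | Reason |
|---|---|---|
| Year earlier | 8 | start month at or after the Day 1 month triggers bullet 1; in the later-end-year row bullet 2 can also give prior |
| Same year, month missing | 7 | equal year triggers bullet 1 |
| Same year, month earlier | 7 | equal year triggers bullet 1 |
| Same year, same month | 6 | equal year and equal month trigger bullet 1 |
| Year missing | 1 | end in a later year but an earlier calendar month triggers bullet 2 |

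Total: 8 + 7 + 7 + 6 + 1 = **29 of 48**. Where a category covers several calendar months, the conflict arises for some of them.

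**Both bullets apply.** End year earlier: 1 cell. End in the same year, earlier month: 3. End year later, with an earlier calendar month: 7. Total: **11 of 48**.

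**Worked records.**

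- Day 1 November 2020, start March 2015, end January 2021. Bullet 1 fails (March precedes November; 2015 precedes 2020). Bullet 2 applies (January precedes November), giving prior. The table gives Prior/Con, so the medicine would be lost from the concomitant summary.
- Day 1 June 2020, start 2020 with month unknown, end May 2020. Bullet 1 applies (2020 equals 2020) and so does bullet 2 (May precedes June). The table gives Prior.
- Day 1 30 June 2020, start December 2018, end June 2020. Only bullet 1 applies (December follows June), giving concomitant. The table gives Prior/Con, so only the prior summary changes.

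**Year-first reading, equality kept.** The overlap between bullets falls from 11 cells to 0, and the disagreements from 29 to **6**: the whole column for a start in the Day 1 month with the day unknown. The bullets give concomitant; the table gives Prior/Con.

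**Effect on the summaries.** Prior/Con medicines enter both summaries, so swapping Prior/Con for Con never alters the concomitant summary. In printed order it can change in 6 cells:

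- 4 where the table says Prior and bullet 1 can give Con. Bullet 2 also applies to these records, so the error depends on an order that the SAP does not state.
- 2 where the table says Prior/Con and bullet 2 can give Prior. Both need an end date in a calendar year after Day 1.

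The other 29 − 6 = 23 affect the prior summary alone.

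**If bullet 2 took precedence.** The 4 cells above would agree with the table, and 3 more in the later-end-year row could disagree: 29 − 4 + 3 = 28. All 8 cells of that row could then change the concomitant summary.

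**The case against.** The intended meaning is visible. The bullets speak of dates clearly before or after Day 1, and the table spells out the cells with the year first. The rule for treatment-emergent adverse events in the same section uses the same order ("If Month of AE start date < Month of Study Day 1, set it as non TEAE" sits under the same-year branch), although it assigns only TEAE or non-TEAE and says nothing about medication labels. A careful programmer would probably follow the table, and on a year-first reading both worked mislabellings in the concomitant summary disappear. This stands as a limit on the practical risk. It does not remove the conflict: 6 cells still disagree, and the section names no governing rule.

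Three stronger readings are tempting, and the documents do not support them.

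- **That deviation review or the per-protocol set is affected.** Urate-lowering drugs are prohibited from Visit 2 (Protocol 7.3), so a wrong label may look like a hidden or false violation. But SAP 5.2 leaves deviations to the clinical research physician or designee under standard procedure, and SAP 4.4.4 settles the deviations that matter for the per-protocol set at a blinded data review meeting. Neither refers to this label.
- **That stopped urate-lowering drugs will often be mislabelled.** They are to be stopped the day prophylaxis begins (schedule of assessments, footnote 4), and Protocol 9.1.7 collects start and stop dates. Nothing suggests that these stop dates will be partial. A complete stop date before Day 1 is not concomitant under SAP 7.1.2.
- **That about 23% of records are exposed.** For Day 1 dates in 2020, Day 84 falls in the next year for 83 of 366 (22.7%). That is a share of start dates, not of mislabelled records. The documents give no rate of partial dates.

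**Conclusion.** The bracketed conditions in SAP 14.3.2 are wrong as written. Taken literally and in printed order, they conflict with the table in 29 of 48 applicable cells; read year-first, in 6. The counts are of table cells, not patients or records, and they assume eight start-date columns. The number of records affected cannot be derived from the documents.

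The consequence is confined to records with incomplete dates in the prior and concomitant medication summaries of SAP 7.1.1 and 7.1.2. The primary serum uric acid endpoint does not use the label. Flare-rescue matching in SAP 8.1.2 uses the medication dates themselves. No date is altered; only a category is at issue. Severity is at the nice-to-have level.

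**What to change.** Delete the bracketed month and year conditions from the first two bullets of SAP 14.3.2 and state that the table is the sole rule for incomplete medication dates. Keep every cell of the table, including Con for a start on the Day 1 day, in a later month of the same year, or in a later year. A shorter paraphrase that sends every equal month to Prior/Con would contradict the day-equal column, and SAP 7.1.2, which counts a medication taken on Day 1 as concomitant.

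The cost is one wording change and one check that the derivation program follows the table. No data collection or other analysis changes.
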